## 8. DATA SAFETY MONITORING PLAN

---

Oversight for this study will be provided by the Principal Investigators, Drs. [name] and [name], with delegation of responsibilities to designated study personnel. Study PIs will ensure all entry criteria are met prior to the initiation of the protocol, and all study procedures and reporting of adverse events are performed according to the IRB-approved protocol.

Institutional support of trial monitoring will be in accordance with the Fred Hutch/University of Washington Cancer Consortium Institutional Data and Safety Monitoring Plan. Under the provisions of this plan, Fred Hutch Clinical Research Support coordinates data and compliance monitoring conducted by consultants, contract research organizations, or Fred Hutch employees unaffiliated with the conduct of the study. Independent monitoring visits occur at specified intervals determined by the assessed risk level of the study and the findings of previous visits per the institutional DSMP. Study participants are prostate cancer patients undergoing ADT + RT, in whom the study intervention is non-therapeutic. The study is low risk, per the Consortium DSMP guidelines.

### 8.1 Adverse Event Reporting

All adverse events related to the study procedures will be fully documented on the appropriate case report form(s) and entered in a study database. For each adverse event, the investigator will provide the onset, duration, intensity, treatment required, and outcome, including documentation of need for premature termination of any study procedures. Anticipated adverse events for this study are expected to be very minimal since the diet and physical activity intervention activities have been safely used in many previous intervention studies without incident. Despite the low risk for adverse events, all study staff and investigators will carefully monitor and document any adverse events, which could include the following: bruising or fainting during the blood draws, injury from using the exercise equipment in the PHS Exercise Laboratory, injury from exercise at home (such as a fall) or a medical event during exercise in the PHS exercise Laboratory. Serious Adverse Events will be reported within to the Principal Investigator within 24 hours. Adverse event reporting to the IRO will occur within the required period of time depending on the nature and severity of the event.

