#### 4.3 Mid-Study Questionnaire (both sites)

At the mid-point of study (month 3), participants will be asked to complete the quality of life/fatigue questionnaire (Triple A QOL questionnaire). This questionnaire can be completed remotely via a web-survey link, on paper (via mail) or in person (if the study mid-point coincides with the participants' second treatment visit or a nutrition intervention visit)..

#### 4.4 Clinic Visit 2

**UW (at Fred Hutch):** Clinic Visit 2 will occur at the end of the study, 6 months after Clinic Visit 1. In preparation for Clinic Visit 2, participants will be mailed (or given) the end of study Food Record (Food Record, Serving size booklet), stool collection kit, and instructions (Triple-A CV2 instructions, Triple-A Stool collection) to prepare for the visit. Participants will be asked to complete the Food Record and collect a small amount of stool, and bring both to Clinic Visit 2. At Clinic Visit 2, study staff will measure weight and waist circumference, conduct a DXA scan and collect fasting blood. Participants will complete the final questionnaires on physical activity and quality of life (Triple-A QOL questionnaire, Triple-A PA questionnaire), and will complete an End of Study questionnaire (Triple-A Exit Survey). Participants assigned to the control arm will also be given a copy all of the intervention materials and the study dietitian will review the materials.

**VAPSHCS (at VAPSHCS):** Clinic Visit 2 will occur at the end of the study, 6 months after Clinic Visit 1. In preparation for Clinic Visit 2, participants will be mailed (or given) the end of study Food Record, stool collection kit, and instructions to prepare for the visit. Participants will be asked to complete the Food Record and bring it to Clinic Visit 2. At Clinic Visit 2, study staff will measure weight and waist circumference, conduct a DXA scan and collect fasting blood. Participants will complete the final questionnaires on physical activity and quality of life (Triple-A QOL questionnaire, Triple-A PA questionnaire). Finally, participants assigned to the control arm will be given a copy all of the intervention materials and the study dietitian will be scheduled for a brief teleconference with the study dietitian to review the materials.

If requested, a participant may receive a copy of their DEXA scan results.

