## 4.6 Intervention

Intervention arm participants will attend 10 sessions with a registered dietitian over six-months to receive instruction on a modified-Dietary Approaches to Stop Hypertension (DASH) diet. In addition, participants will attend two one-on-one sessions with an exercise physiologist to receive instruction on aerobic physical activity and strength/resistance training. Participants will also be offered the opportunity to complete up to 21 additional supervised exercise sessions at either the Fred Hutch Prevention Center (PC) or VA Clinical Research Unit (CRU). The following materials will be used to provide Intervention instruction to participants in the Intervention arm: Triple-A Nutrition Intervention; Triple-A PA Intervention; Triple-A Supplemental Nutrition\_V1; Triple-A Supplemental PA\_V1.

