## 4.7 Controls.

Written information (Triple-A Controls) on standard healthy lifestyle recommendations will be provided along with a 20-30 minutes individual session with a dietitian including 1) US Dietary Guidelines ([www.dietaryguidelines.gov](http://www.dietaryguidelines.gov)); 2) Activity goal of 30 minutes of physical activity 5 days/week; and 3) Discussion of the health benefits of weight maintenance.

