the study coordinator and will be encouraged to call with any problems at any time. Participants will be encouraged to call 911 in case a life-threatening emergency occurs; such an event is unlikely, and it would be extremely unlikely to be related to the study procedures.

3. We will make every effort to schedule participants to come to the FHCRC at times that are convenient for them. This includes all sessions with the study dietitian and exercise specialist.
4. To minimize the risk of breach of confidentiality, we will make sure that all health information and records are labeled with a study identification number only. Personally identifiable information will be kept physically separate from any health information, and only one computer file will link the study identification number to the personally identifiable information such as name, address, telephone.

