### 8.2 Plan for safety review

The PIs will perform a cumulative review of all adverse events and premature terminations review every 6 months after study initiation.

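### Section 8.1 gives two different rules for which adverse events are recorded, and neither arm has a described event question although scheduled staff contact differs sharply, so event counts by arm would be open to ascertainment bias.

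*Combined protocol and SAP*

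**What the plan says.** **Recording.** Section 8.1 opens with the rule that "All adverse events related to the study procedures will be fully documented on the appropriate case report form(s") and entered in a study database. Further on it says that "all study staff and investigators will carefully monitor and document any adverse events". It follows this with examples, among them injury during home exercise. Serious events go to the Principal Investigator within 24 hours, with no relatedness condition.

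**Review and reporting.** Section 8.2 states: "The PIs will perform a cumulative review of all adverse events and premature terminations", every six months. Section 8.3 requires the annual report to give the number of adverse events and how each was handled. Neither section limits this to related events.

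**Contact in the intervention arm.** Section 4.6 schedules 10 dietitian sessions and two exercise physiologist sessions. In addition, "Participants will also be offered the opportunity to complete up to 21 additional supervised exercise sessions".

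**Contact in the control arm.** Section 4.7 gives controls written material and one dietitian session of 20 to 30 minutes, which Section 4.2 places after the Clinic Visit 1 procedures. Their advice includes this item: "Activity goal of 30 minutes of physical activity 5 days/week".

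**Contact in both arms.** At month 3, under Section 4.3, "participants will be asked to complete the quality of life/fatigue questionnaire", by web, by mail or in some cases in person. Clinic Visit 2 follows at six months. Section 6.2 invites men who have left the clinic to telephone staff with any problem.

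**The concern.** Two sites will apply Section 8.1, and it can be read in two ways. If its opening sentence governs the database, relatedness is judged before an event is entered. The six-monthly review and the annual count would then rest on a filtered set, even though both are described as covering every event. The section gives no criteria for relatedness, no definition of an adverse event and no collection window. It does not name who judges relatedness. It also does not say what counts as a study procedure for a control man who is hurt while following his activity advice.

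The second difficulty is detection. With no scheduled question about events, staff learn of them when a man mentions one at a session or telephones. Only intervention men have sessions between the two clinic visits. Section 6.3 says the pilot will inform the design and endpoints of a full trial. If someone tabulates adverse events by arm for that purpose, part of any difference would reflect how often each arm was seen.

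**Working it through.** The plan states no adverse event rate and no safety power, so there is no planned figure to reproduce. The check is a reading of the text and a count of contacts.

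**1. The recording rules side by side**

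| Place | What is covered | Limited to related events? |
|---|---|---|
| 8.1, opening sentence | Case report form and database entry | Yes |
| 8.1, later sentence | Monitoring and documentation by staff | No |
| 8.1, serious events | Report to the Principal Investigator in 24 hours | No |
| 8.2 | Six-monthly cumulative review | No |
| 8.3 | Annual report, including number of events | No |

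The only row that names a form and a database is the only row with the limit. The others presuppose a complete record that the first does not promise. There is also a smaller mismatch. Section 6.1 names a medical event during exercise at home as a risk, while the examples in 8.1 mention a medical event only for exercise in the laboratory. That list is introduced as illustrative, so it does not exclude the home event.

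**2. Where a man would be asked about events**

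- Clinic Visit 2 (4.4): weight, waist, DXA, blood, physical activity and quality-of-life questionnaires. No event question is described.
- Month 3 (4.3, 5.1.3): quality of life and fatigue only.
- Exit survey (Section 5): experience in the study and, for intervention men, challenges with the intervention. It is not described as an event form.
- Unscheduled: the man telephones (6.2).

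**3. Scheduled staff sessions after the baseline session and before Clinic Visit 2**

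- Intervention, required: 10 dietitian + 2 physiologist = 12.
- Intervention, with all optional sessions: 12 + 21 = 33.
- Control: 0.
- Both arms: the month-3 questionnaire.

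Section 2.1 puts physiologist and dietitian sessions on the same day. If both physiologist sessions are paired in this way, the 12 required sessions fall on 10 separate days.

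Intervention staff also have reason to hear of symptoms. Section 4.6 has the exercise regimen altered when a man reports undue fatigue or treatment-related symptoms, and Section 4.8 adds check-ins and daily logs.

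**4. Exercise exposure in controls**

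The control goal is 30 minutes × 5 days = 150 minutes per week. The intervention aerobic goal in 4.6 is at least 150 minutes per week. Controls lack the resistance programme, but they are not free of exercise-related events.

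**5. Direction and precision**

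Expected recorded events in an arm = 10 × true risk × probability that an event is captured. If the true risks are equal, the ratio of recorded counts equals the ratio of the two capture probabilities. The documents give no capture probabilities, so the size of the bias cannot be derived from them. Its likely direction can: capture should be lower where contact is lower, which is the control arm.

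For scale, suppose capture were perfect and no events occurred in 10 men. The one-sided 95% upper bound on the risk would be 1 − 0.05^(1/10) = 0.259, or 25.9%. Any contrast between arms of 10 would be imprecise in any case.

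**The case against.** The strongest reply is that the opening of 8.1 is loose drafting. The same section commits staff to documenting any event, and 8.2 and 8.3 cover all of them. No between-arm safety analysis appears among the aims, the endpoints or Section 7. The trial is a 20-man pilot that Section 8 classes as low risk. The case report forms, questionnaires and institutional monitoring plan are not reproduced, so an event question may exist in one of them.

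Much of this stands, and it rules out several stronger readings that a reader might infer:

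- *Only related events are ever recorded.* This takes one sentence of 8.1 alone. The text is contradictory on the point and does not settle on a filter.
- *Home exercise injuries are under-recorded.* Section 8.1 lists them expressly, and the arm given the exercise programme is also the arm seen often.
- *Coronary events, strokes or sudden deaths are excluded.* The serious-event rule carries no relatedness limit. It does not say how staff come to know of an event, so late or missed awareness is possible, but exclusion by rule is not shown.
- *Section 6.2 pre-classifies emergencies as unrelated.* Its remark that "such an event is unlikely, and it would be extremely unlikely to be related to the study procedures" is an expectation in a risk section. It does not classify events.
- *The arms' safety data cannot be compared.* A comparison would be open to bias and imprecise, which is a weaker statement, and none is planned.

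It is also true that the month-3 questionnaire can be completed in person when it coincides with a second treatment visit, which is open to controls.

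The reply does not remove the conflict between the sentences of 8.1, and it does not supply a common event question. A low-risk classification does not tell two sites which rule to follow.

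**Conclusion.** The point holds in a limited form. Section 8.1 is internally inconsistent about which events reach the case report form and database. No described assessment asks either arm about events, and scheduled sessions between the visits number 12 to 33 against none. Adverse event counts by arm would be open to ascertainment bias. The likeliest losses are control-arm events and non-serious events judged unrelated.

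This rests on two assumptions: that the forms and the monitoring plan not shown contain no common event inquiry, and that more staff contact means more events come to light. The size of the bias is unknown. No planned analysis is invalidated, so this is a moderate reporting weakness. It is worth correcting because the correction is cheap and the pilot is meant to inform a larger trial.

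**What to change.** 1. In 8.1, replace the opening rule with one rule for both sites: every adverse event from Clinic Visit 1 through Clinic Visit 2 is entered on the case report form and in the database regardless of relatedness. Relatedness is then recorded as a separate field.
2. Ask the same short question set in both arms, for example any fall, injury, cardiovascular event, or hospital or emergency visit since last asked. Attach it to the existing month-3 questionnaire and repeat it at Clinic Visit 2.
3. Base any by-arm adverse event summary on those two time points. List events volunteered at intervention sessions separately.

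The cost is a wording change and a few added questions at two contacts that already exist. The drawback is that more unrelated events, including those attributed to RT or ADT, must be recorded for 20 men.

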### 8.2 Plan for safety review

The PIs will perform a cumulative review of all adverse events and premature terminations review every 6 months after study initiation.

### 8.3 Plan for annual reporting

A summary of the investigation including all adverse events and how they were handled, enrollment, drop-outs and reason for discontinuation and any protocol modifications will be provided to the IRB on an annual basis. Annual Reports will contain:

- a. The number of adverse events and an explanation of how each event was handled
- b. The number of complaints and how each complaint was handled
- c. The number of subject withdrawals and an explanation of why the subject withdrew or was withdrawn
- d. The number of protocol deviations and how each was handled

#### 8.4 Monitoring for data integrity and safety

Monitoring for data integrity and safety will be the responsibility of the investigators. Investigators will include the following in routine monitoring review: A) Validity and integrity of data: Data are checked for missing, unusual, or impossible values when they are entered into the study's computer database. B) Enrollment rate relative to expectation: Early lags in recruitment will be rectified with increased recruitment efforts so that recruitment will be completed on time. The investigators will monitor this closely to ensure full enrollment of appropriate participants. C) Retention of participants and adherence to protocol: The investigators will monitor retention and adherence to study protocol. Adherence to the intervention will be monitored via participant weight, nutrition and physical activity visits.

